#### Hematology

Hemoglobin, hematocrit, erythrocyte sedimentation rate, red blood cell count, white blood cell count with differential and platelet count will be measured.

#### Clinical chemistry

#### Corporate Confidential Information

Sodium, potassium, uric acid, chloride, albumin, calcium, magnesium, phosphate, alkaline phosphatase, amylase, bicarbonate, indirect bilirubin, direct bilirubin, total bilirubin, blood urea nitrogen, LDH, GGT, AST, ALT, , glucose, total cholesterol, triglycerides, C-reactive protein, t

If the total bilirubin concentration is increased above 1.5 times the upper limit of normal, direct and indirect reacting bilirubin should be differentiated.

#### Coagulation

PT (reported as INR), aPTT.

## Urinalysis

Urine test by dipstick e.g. Combur9: leucocytes, nitrite, pH, protein, glucose, ketones, urobilinogen, bilirubin, blood/ hemoglobin, specific gravity.

If the dipstick result is positive for protein, nitrite, leucocytes and/or blood, the sample will be sent for microscopic analysis of WBC, RBC and casts.

## Hepatitis screen

All subjects will be tested for Hepatitis B and Hepatitis C seropositivity at the screening visit. Hepatitis B will be evaluated using the Hepatitis B surface antigen (HBsAg). Screening for Hepatitis C will be based on HCV antibodies. Patients with a positive Hepatitis C antibody test should have HCV RNA levels measured.

Results will be available as source data and will not be recorded within the clinical database.

### 8.4.5 Electrocardiogram (ECG)

ECG evaluations will be obtained at specific time points specified in the [Assessment Schedules](#).

A standard 12-lead ECG will be performed with the subject in a supine position. Interpretation of the tracing must be made by a qualified physician and documented on the ECG and in the ECG section of the source document. Each ECG tracing should be labeled with the

- study number
- patient initials
- patient number
- date

and kept in the source documents at the study site. Clinically significant abnormalities should be recorded on the relevant medical history eCRF page prior to informed consent signature and on the Adverse Events page thereafter. Clinically significant findings must be discussed with the sponsor.

### 8.4.6 Immunogenicity

All patients dosed with CLR325 will have blood samples analyzed for antibodies targeting CLR325. In addition, cross-reactivity of anti-drug antibodies towards endogenous apelin will be assessed. Anti-CLR325 and anti-apelin antibodies will be assessed in serum by an immunoassay. Due to the size of CLR325 and apelin, all anti-drug antibodies are expected to possess neutralizing capacity.

#### Corporate Confidential Information

The timing of immunogenicity sampling is provided in the [Assessment Schedule](#), and details of sample collection are provided in the Laboratory Manual.

All blood samples will be taken by either direct venipuncture (other than the vein used for dose administration) or an indwelling cannula inserted in a forearm vein. All samples will be given a unique sample number and a collection number (as listed in Blood log within the

SOM). The actual sample collection date and time will be entered on the PK blood collection page of the source documentation. Sampling problems will be commented in the eCRF system.

#### **8.4.7 Alcohol test and drug screen**

Patients will be tested for substances of abuse (e.g., alcohol, amphetamines, barbiturates, benzodiazepines, cannabinoids, cocaine, and opiates).

Results will be available as Source data and will not be recorded within the clinical database.

#### **8.4.8 AICD interrogation**

If patients have an automatic implantable cardioverter defibrillator (AICD) in place, the device will be interrogated at the baseline visit and at the end of study visit to assess any arrhythmias that occurred during the entire study period. The information gathered from the interrogation (e.g., number of runs of ventricular tachycardia) will be recorded in the eCRF.

#### **8.4.9 Cardiac Holter and telemetry monitoring**

Patients will be connected to a Holter monitor to gather data on heart rate and cardiac arrhythmias that occur during the treatment period of the study. The monitoring will begin at approximately 1 hour prior to the start of study drug infusion and disconnected prior to inpatient discharge. Given the time required to analyze Holter recordings, Holter results will not be available to site investigators prior to patient discharge. However, in addition to Holter monitoring, patients will also be monitored via real time cardiac telemetry to allow site staff to immediately detect the occurrence of any cardiac arrhythmias.

#### **8.4.10 Fluid input and output**

Fluid intake and output during the treatment period will be recorded in the appropriate section of the eCRF.

### **8.5 Pharmacokinetics**

Pharmacokinetic (PK) samples will be obtained and evaluated in all subjects. Untreated samples (placebo) will not be analyzed. The plasma samples will be analyzed to quantify CLR325 using a validated LC-MS/MS method.

For standard pharmacokinetic abbreviations and definitions see the list provided at the beginning of this protocol. The following pharmacokinetic parameters will be determined using the actual recorded sampling times and non-compartmental method(s) with Phoenix WinNonlin (Version 6.4 or higher): Cmax, Tmax, AUC0-18h, AUClast, AUC0-28h, AUCinf, T1/2, CL (CLR325 only), Vss (CLR325 only), CLr, and Ae0-28 from the plasma concentration-time or urine concentration and collection volume data. The renal clearance (CLr) will be determined based on AUC and Ae available for the same time period.

The linear trapezoidal rule will be used for AUC calculation. Regression analysis of the terminal plasma elimination phase for the determination of T1/2 will include at least 3 data points after Cmax. If the adjusted R^2 value of the regression analysis of the terminal phase will be less than 0.75, no values will be reported for T1/2, AUCinf, Vss (CLR325 only), and CL (CLR325 only).

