### 2.2 Secondary objective(s)

Secondary objective(s)	Endpoints related to secondary objective(s)

To determine the pharmacokinetics of CLR325, and the active metabolite, CQJ295, during an 18-hour i.v. infusion of CLR325 in heart failure patients.

	

Plasma and urine pharmacokinetic parameters of CLR325 and CQJ295 (Cmax, Tmax, AUC0-18h, AUClast, AUC0-28h, AUCinf, T1/2, CL (CLR325 only), Vss (CLR325 only), CLr, and Ae0-28 during the course of an 18-hour infusion and post-infusion in heart failure patients.

To determine the immunogenicity of an 18-hour i.v. infusion of CLR325 in heart failure patients.

	

Treatment related titer of anti-CLR325 and anti-apelin antibodies after infusion of CLR325 in heart failure patients.

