### 8.5.3 PK urine collection (28-hour urine collection)

PK urine samples will be collected to assess renal clearance of CLR325 and its active metabolite, CQJ295. Twenty-eight (28) hour cumulative urine will be collected post the start of the infusion. The urine collected from each voiding will be refrigerated (4°C). The entire collection over 28 hours will be made homogenous and the final volume and pH value will be recorded before a sample for PK analysis is taken.

For details on the sample numbering, collection, processing, labeling, and shipment instructions, see laboratory manual. The collection period is also described in the [Assessment Schedule](#). Relevant sample information will be entered on the PK urine collection summary page of the source documentation. Sampling problems will be noted in the relevant field of the source documentation.

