### **11.5.3 Pharmacokinetics**

CLR325 plasma concentration data will be listed by treatment, subject, and visit/sampling time point. Descriptive summary statistics will be provided by treatment and visit/sampling time point, including the frequency (n, %) of concentrations below the LLOQ and reported as zero.

Summary statistics will include mean (arithmetic and geometric), SD, CV (arithmetic and geometric), median, minimum and maximum. An exception to this is Tmax where median, minimum and maximum will be presented. Concentrations below LLOQ will be treated as zero in summary statistics and for PK parameter calculations. A geometric mean will not be reported if the dataset includes zero values. Pharmacokinetic parameters will be calculated as described in [Section 8.5](#) and will be listed by treatment and subject.

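### The plasma assay sentence in Section 8.5 and the plasma concentration sentence in Section 11.5.3 omit the active metabolite CQJ295, whose plasma pharmacokinetics Section 2.2 makes a secondary endpoint

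*Protocol*

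**What the plan says.** **Objective and endpoint.** Protocol Section 2.2 sets the secondary objective as "To determine the pharmacokinetics of CLR325, and the active metabolite, CQJ295, during an 18-hour i.v. infusion of CLR325 in heart failure patients", and the synopsis carries the same objective. The matching endpoint opens with "Plasma and urine pharmacokinetic parameters of CLR325 and CQJ295" and then lists the parameters, two of them restricted to CLR325.

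**Assay and parameters.** Section 8.5 describes the bioanalysis of plasma in one sentence: "The plasma samples will be analyzed to quantify CLR325 using a validated LC-MS/MS method". It then repeats the parameter list with the same two restrictions, ending: "CL (CLR325 only), V ss (CLR325 only), CL r , and Ae 0-28 from the plasma concentration-time or urine concentration and collection volume data". For renal clearance it adds: "The renal clearance (CL r ) will be determined based on AUC and Ae available for the same time period".

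**Urine.** Section 8.5.3 names both analytes: "PK urine samples will be collected to assess renal clearance of CLR325 and its active metabolite, CQJ295".

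**Analysis.** Section 11.5.3 says "CLR325 plasma concentration data will be listed by treatment, subject, and visit/sampling time point" and follows with descriptive summaries by treatment and sampling time. For parameters it names no analyte and points back to Section 8.5: "Pharmacokinetic parameters will be calculated as described in" that section. Section 11.4.2 provides for descriptive summaries of the pharmacokinetic results per treatment, again without naming an analyte.

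**The concern.** The endpoint needs metabolite concentrations in plasma. The two sentences that govern plasma concentrations, one on the assay and one on the listing and summary, mention only the parent. No other sentence in the protocol has CQJ295 quantified in plasma, whereas the urine section names it explicitly.

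CQJ295 is described as active, and the primary objective is safety and tolerability. If a laboratory set up its work from the assay sentence alone, exposure to an active moiety would be unknown when adverse events are interpreted. Most of the metabolite part of a named secondary endpoint would also be empty. An analysis plan written later could not repair this, because it cannot summarise a concentration that was not measured. The protocol does not say whether stored plasma could be assayed for CQJ295 afterwards.

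**Working it through.** The plan gives no figure to reproduce. The check is a comparison of sections and a count.

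**1. Which parameters the endpoint requires (Section 2.2, repeated in Section 8.5).**

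| Parameter | CLR325 | CQJ295 | Needs that analyte in plasma? |
|---|---|---|---|
| Cmax | yes | yes | yes |
| Tmax | yes | yes | yes |
| AUC0-18h | yes | yes | yes |
| AUClast | yes | yes | yes |
| AUC0-28h | yes | yes | yes |
| AUCinf | yes | yes | yes |
| T1/2 | yes | yes | yes |
| CL | yes | no | yes |
| Vss | yes | no | yes |
| CLr | yes | yes | yes, through AUC |
| Ae0-28 | yes | yes | no, urine only |

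- Parameters listed: 11.
- Required for CQJ295: 11 − 2 (CL and Vss) = 9.

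**2. Which CQJ295 parameters need plasma CQJ295.**

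- Cmax, Tmax, four AUCs and T1/2: 1 + 1 + 4 + 1 = 7 direct plasma parameters.
- CLr adds one. Section 8.5 bases it on AUC and Ae over the same period, so CLr = Ae / AUC for the same analyte and interval, and the AUC comes from plasma.
- Total: 7 + 1 = 8 of 9. Only Ae0-28 survives without a plasma assay of the metabolite.

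**3. Share of the whole pharmacokinetic endpoint.**

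- Analyte-by-parameter combinations: 11 (CLR325) + 9 (CQJ295) = 20.
- Lost under a literal reading of the assay sentence: 8 / 20 = 40%.

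**4. Where each section stands on plasma CQJ295.**

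| Section | Plasma CQJ295 |
|---|---|
| 2.2 endpoint | required |
| 8.5 parameter list | required by implication, since only CL and Vss are confined to the parent |
| 8.5 assay sentence | not named |
| 8.5.3 urine | required by implication, since its purpose includes CQJ295 renal clearance |
| 11.5.3 concentration sentence | not named |
| 11.5.3 parameter sentence | not restricted by analyte |
| 11.4.2 general summary | not restricted by analyte |

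The text of Sections 8.5 and 11.5.3 carries no redaction mark, so blacked-out wording does not explain the gap.

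**The case against.** The strongest reply is that this is one incomplete sentence and that the rest of the protocol makes the intention plain. The assay sentence does not say that CLR325 is the only analyte. Where the protocol wants to exclude the metabolite it says so, as it does for CL and Vss in the same section. Those restrictions make sense only if the other plasma parameters are determined for CQJ295 too. The urine section names no assay method for either analyte, and nobody would conclude that urine goes unassayed. Sample handling is deferred to a laboratory manual, which is not at hand.

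Most of this stands, and it rules out three stronger readings that a reader might draw:

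- **That the protocol decides to assay plasma for the parent alone.** The text does not say so, and the parameter list in Section 8.5 points the other way.
- **That Section 11.5.3 reports only CLR325.** Only its concentration sentence names the parent. Its parameter sentence, and the general summary in Section 11.4.2, carry no analyte restriction.
- **That half of the pharmacokinetic objective would have no data.** The count is 8 of 20 combinations, it applies only under a literal reading of one sentence, and CQJ295 Ae0-28 would still be obtained.

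The objection does not remove the inconsistency. The point does not rest on silence: the protocol states a plasma assay, and that statement does not cover its own endpoint. Section 8.5.1 refers to the laboratory manual for collection, processing, labelling and shipment, not for the choice of analyte. Nor can unrestricted reporting of parameters create the concentrations from which they are calculated.

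**Conclusion.** The protocol is wrong as written on a point of internal consistency. Sections 2.2 and 8.5 require plasma pharmacokinetics of CQJ295, while the assay sentence in 8.5 and the concentration sentence in 11.5.3 name CLR325 alone. A drafting omission is the most likely explanation.

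The loss of eight CQJ295 parameters is conditional on the assay sentence being executed literally. If the laboratory works from the endpoint instead, nothing is lost and only the text is at fault. The conclusion assumes that no text outside the protocol, such as the laboratory manual, already specifies a plasma assay for CQJ295. If one does, the practical risk disappears, but the protocol sentences should still be brought into line. The matter is minor in severity and worth correcting because the correction is so cheap.

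**What to change.** In Section 8.5, state that plasma is assayed for both CLR325 and CQJ295 with validated methods. In Section 11.5.3, make the conforming edit so that the concentration listing and summary cover both analytes. The parameter sentences in Sections 11.5.3 and 11.4.2 can stay as they are.

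If plasma CQJ295 is not intended, restrict the CQJ295 endpoint in Section 2.2 to urinary Ae0-28. The parameter restrictions in Section 8.5 and the stated purpose of the urine collection in Section 8.5.3 would then have to follow, since CQJ295 renal clearance could no longer be derived.

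The first option costs a few words. It adds no samples or visits, and the only assay involved is one that the endpoint already requires.

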### 8.5.1 PK blood collection

For details on PK blood collection and processing, labeling, and shipment instructions, see laboratory manual. The laboratory manual must be strictly adhered to. PK sample collection times are described in the [Assessment Schedule](#). Samples will be collected via syringe that will be connected to an i.v. catheter or butterfly needle and transferred into a customized tube that will be supplied by the central laboratory. These customized tubes are not sterile and must not be filled by direct phlebotomy.

The exact clock time of dosing, as well as actual sample collection date and time will be entered on the PK blood collection summary page of the source documentation. Sampling problems will be noted in the relevant field of the source documentation.

### 8.5.2 PK assessments

See Sample Blood log tables in the Site Operations Manual.

Deviations for the following assessment times are acceptable based on logistical and operational considerations:

**Table 8-2 Permitted assessment windows**

Activity	0hr	Post start of infusion
PK blood collection time-points	Within 60 min prior to start of infusion	± 5 min up to 28 hours

Every effort will be made to take the pharmacokinetic sample at the protocol specified time. Other assessments, e.g., ECG, vital signs etc. should be taken after the PK sample.

### 8.5.3 PK urine collection (28-hour urine collection)

PK urine samples will be collected to assess renal clearance of CLR325 and its active metabolite, CQJ295. Twenty-eight (28) hour cumulative urine will be collected post the start of the infusion. The urine collected from each voiding will be refrigerated (4°C). The entire collection over 28 hours will be made homogenous and the final volume and pH value will be recorded before a sample for PK analysis is taken.

For details on the sample numbering, collection, processing, labeling, and shipment instructions, see laboratory manual. The collection period is also described in the [Assessment Schedule](#). Relevant sample information will be entered on the PK urine collection summary page of the source documentation. Sampling problems will be noted in the relevant field of the source documentation.

## **8.6 Other assessments**

No additional tests will be performed on subjects entered into this study.

**Corporate Confidential Information**

## Corporate Confidential Information

### 9 Safety monitoring

#### 9.1 Adverse events

An adverse event (AE) is any untoward medical occurrence (i.e., any unfavorable and unintended sign [including abnormal laboratory findings], symptom or disease) in a subject or clinical investigation subject after providing written informed consent for participation in the study. Therefore, an AE may or may not be temporally or causally associated with the use of a medicinal (investigational) product.

The occurrence of adverse events should be sought by non-directive questioning of the patient at each visit during the study. Adverse events also may be detected when they are volunteered by the patient during or between visits or through physical examination, laboratory test, or other assessments.

Abnormal laboratory values or test results constitute adverse events only if they fulfill at least one of the following criteria:

- they induce clinical signs or symptoms,
- they are considered clinically significant,
- they require therapy.

Clinically significant abnormal laboratory values or test results should be identified through a review of values outside of normal ranges/clinically notable ranges, significant changes from baseline or the previous visit, or values which are considered to be non-typical in patients with underlying disease. Investigators have the responsibility for managing the safety of individual subject and identifying adverse events. Alert ranges for liver related events are included in [Section 9.3](#).

Adverse events must be recorded on the Adverse Events eCRF for patients that pass screening and enter into the study. The adverse events should be reported according to the signs, symptoms or diagnosis associated with them, and accompanied by the following information:

1. The severity grade AE grade
  - mild: usually transient in nature and generally not interfering with normal activities
  - moderate: sufficiently discomforting to interfere with normal activities
  - severe: prevents normal activities
2. Its relationship to the study treatment

3. Its duration (start and end dates) or if the event is ongoing an outcome of not recovered/not resolved should be reported.
4. Whether it constitutes a serious adverse event (SAE). See [Section 9.2](#) for definition of SAE
5. Action taken regarding study treatment. All adverse events should be treated appropriately. Treatment may include one or more of the following:
  - no action taken (i.e. further observation only)
  - study treatment dosage adjusted/temporarily interrupted
  - study treatment permanently discontinued due to this adverse event
  - concomitant medication given
  - non-drug therapy given
  - subject hospitalized/subject's hospitalization prolonged
6. Its outcome (not recovered/not resolved; recovered/resolved; recovering/resolving, recovered/resolved with sequelae; fatal; or unknown)

Once an adverse event is detected, it should be followed until its resolution or until it is judged to be permanent, and assessment should be made at each visit (or more frequently, if necessary) of any changes in severity, the suspected relationship to the study drug, the interventions required to treat it, and the outcome.

Information about common side effects already known about the investigational drug can be found in the Investigator Brochure (IB) or will be communicated between IB updates in the form of Investigator Notifications. This information will be included in the subject informed consent and should be discussed with the subject during the study as needed.

The investigator should also instruct each subject to report any new adverse event (beyond the protocol observation period) that the subject, or the subject's personal physician, believes might reasonably be related to study treatment. This information should be recorded in the investigator's source documents, however, if the AE meets the criteria of an SAE, it must be reported to Novartis.

## **9.2 Serious adverse event reporting**

### **9.2.1 Definition of SAE**

An SAE is defined as any adverse event (appearance of (or worsening of any pre-existing) undesirable sign(s), symptom(s) or medical conditions(s) which meets any one of the following criteria:

- is fatal or life-threatening
- results in persistent or significant disability/incapacity
- constitutes a congenital anomaly/birth defect
- requires inpatient hospitalization or prolongation of existing hospitalization, unless hospitalization is for:
  - routine treatment or monitoring of the studied indication, not associated with any deterioration in condition (e.g., worsening of heart failure symptoms)
  - elective or pre-planned treatment for a pre-existing condition that is unrelated to the indication under study and has not worsened since the start of study drug

- treatment on an emergency outpatient basis for an event not fulfilling any of the definitions of a SAE given above and not resulting in hospital admission
- social reasons and respite care in the absence of any deterioration in the patient's general condition
- is medically significant, i.e. defined as an event that jeopardizes the subject or may require medical or surgical intervention.

Life-threatening in the context of a SAE refers to a reaction in which the subject was at risk of death at the time of the reaction; it does not refer to a reaction that hypothetically might have caused death if more severe.

All malignant neoplasms will be assessed as serious under “medically significant” if other seriousness criteria are not met.

Any suspected transmission via a medicinal product of an infectious agent is also considered a serious adverse reaction.

Medical and scientific judgment should be exercised in deciding whether other situations should be considered serious reactions, such as important medical events that might not be immediately life threatening or result in death or hospitalization but might jeopardize the patient or might require intervention to prevent one of the other outcomes listed above. Examples of such events are intensive treatment in an emergency room or at home for allergic bronchospasm, blood dyscrasias or convulsions that do not result in hospitalization or development of dependency or abuse.

All AEs (serious and non-serious) are captured on the CRF, SAEs also require individual reporting to DS&E as per [Section 9.2.2](#).

